### 1. Sexual behaviors

In the **last 12 months** did not:

- Have oral, vaginal or anal intercourse with an HIV-infected partner, or a partner who uses injection drugs
- Give or receive money, drugs, gifts or services in exchange for oral, vaginal or anal sex

**AND**

In the **last 6 months** has abstained from penile/anal or penile/vaginal intercourse,  
OR

In the **last 6 months**:

- Had 4 or fewer partners of the opposite birth sex for vaginal and/or anal intercourse, OR

Is an MSM (person born male with partner(s) born male) who, in the **last 12 months**:

- Had 2 or fewer MSM partners for anal intercourse and had no unprotected anal sex with MSM, OR
- Had unprotected anal intercourse with only 1 MSM partner, within a monogamous relationship lasting at least 12 months (during which neither partner had any other partners). If the monogamous relationship ended, the volunteer may then have had protected anal intercourse with 1 other MSM partner (total 2 or fewer partners in the last 12 months).

Is a transgender person, regardless of the point on the transition spectrum, having sex with men (born male) and/or other transgender persons, who in the **last 12 months**:

- Had 2 or fewer partners for anal or vaginal intercourse, and had no unprotected anal or vaginal sex, OR
- Had unprotected anal or vaginal intercourse sex with 1 partner only within a monogamous relationship lasting at least 12 months (during which neither partner had any other partners). If the monogamous relationship ended, may then have had protected anal or vaginal sex with 1 other partner (total 2 or fewer partners in the last 12 months).

**AND**

Uses or intends to use condoms in situations which may include penile/anal or penile/vaginal intercourse with new partners of unknown HIV status, occasional partners, partners outside a primary relationship, and/or partners known to have other partners.

2. Non-sexual behaviors

In the **last 12 months** did not:

- Inject drugs or other substances without a prescription
- Use cocaine, methamphetamine, or excessive alcohol, which in the investigator's judgment, rendered the participant at greater than low risk for acquiring HIV infection. The investigator's judgment should consider local epidemiologic information about HIV prevalence in the area and community networks.

*A volunteer is NOT appropriate for inclusion if he/she:*

Acquired an STI (i.e. new infection) in the last 12 months:

- Syphilis
- Gonorrhea
- Non-gonococcal urethritis
- Herpes Simplex Virus type 2 (HSV2)
- Chlamydia
- Pelvic inflammatory disease (PID)
- Trichomonas
- Mucopurulent cervicitis
- Epididymitis
- Proctitis
- Lymphogranuloma venereum
- Chancroid
- Hepatitis B

## **Appendix H Adverse events of special interest (AESI)**

AEs of special interest (AESI) for this protocol include those listed below.

- Systemic lupus erythematosus (SLE)
- Systemic scleroderma (SSD) (Systemic sclerosis [SSc]), including diffuse systemic form and CREST syndrome
- Sjogren's syndrome (SS)
- Polymyositis/Dermatomyositis syndrome (PM/DM)
- Raynaud's syndrome
- Antiphospholipid antibody syndrome (APS)
- Idiopathic thrombocytopenic purpura (ITP)
- Crohn's disease
- Ulcerative colitis

1 OVERVIEW

This document describes the Statistical Analysis Plan (SAP) for the analysis of pharmacokinetics data from HVTN 128. The plan will be reviewed and updated prior to additional immunogenicity analyses and before the final safety analysis, with all major revisions of the plan archived.

2 PROTOCOL SUMMARY

2.1 Title

A phase 1 clinical trial to evaluate the safety and pharmacokinetics of VRC-HIVMAB075-00-AB (VRC07-523LS) in the sera and mucosae of healthy, HIV-1-uninfected adult participants

2.2 Design

Multicenter, randomized, unblinded trial

2.3 Study products

- VRC07-523LS: VRC-HIVMAB075-00-AB (VRC07-523LS) is a human monoclonal antibody (mAb) targeted to the HIV-1 CD4 binding site. It was developed by the VRC/NIAID/NIH and manufactured under current Good Manufacturing Practice regulations at the VRC Pilot Plant operated under contract by the Vaccine Clinical Materials Program, Leidos Biomedical Research, Inc., Frederick, MD. VRC07-523LS will be supplied as 10 mL glass vials with a 6.25 ± 0.1 mL fill volume and 3 mL glass vials with a $2.25 \text{ mL} \pm 0.1$ mL fill volume, at a concentration of 100 ± 10 mg/mL.

2.4 Study population

24 healthy, HIV-1-uninfected volunteers aged 18 to 50 years; 24 study product recipients

2.5 Study plans and schema table

Group	N*	Route	VRC07-523LS Dose	Product administration Schedule		
				D0	D112	D224
				W0	W16	W32
1	12	Intravenous (IV) infusion	10 mg/kg	X	X	X
2	12	Intravenous (IV) infusion	30 mg/kg	X	X	X
Total	24					

IV = intravenous infusion

N* = number of participants receiving at least one product infusion

2.6 Duration per participant

12 months of scheduled clinic visits followed by biopsy safety contact 2 weeks after the last scheduled clinic visit

2.7 Estimated total study duration

17 months (includes 5 months for enrollment, and 12 months of scheduled visits)

3.2 Secondary objectives and endpoints

Secondary objective 1:

- To compare dose regimens of VRC07-523LS delivery for their ability to sustain mucosal mAb levels at serial timepoints post repeat administration

Secondary endpoint 1:

- Levels of VRC07-523LS in genital and rectal secretions and tissue at specified timepoints

Secondary objective 2:

- To determine whether ADA can be detected in serum

Secondary endpoint 2:

- Serum concentration of ADA in each group measured at multiple timepoints from baseline through the final study visit

3.3 Exploratory objectives

Exploratory objective 1:

To assess the acceptability and tolerability of repeat mucosal sampling, including secretions and biopsies, for application in future studies

Exploratory objective 2:

To develop predictive mucosal population pharmacokinetic models of VRC07-523LS administered IV

Exploratory objective 3:

To conduct analyses related to furthering the understanding of HIV, monoclonal antibodies, immunology, vaccines, and clinical trial conduct

4 COHORT DEFINITION

Participants will enroll in the study at the first biopsy collection. Only participants who remain in the trial after completion of the first biopsy visit will be randomized. Since enrollment is concurrent with the first biopsy sample collection, all enrolled participants will provide some data regarding the tolerability of mucosal sample collections, regardless of if they are randomized.

Since randomization followed with receiving the first study product administration, all randomized participants will provide some data regarding the safety of the study product. Participants who are randomized but do not receive the study product are released from randomization, so the randomized cohort will consist only of participants who received study product and contribute some data regarding the safety of the study product.

All safety data from randomized participants will be analyzed according to the initial randomization assignment regardless of how many infusions they received. The analysis is a modified intent-to-treat analysis in that individuals who are enrolled but not randomized do not contribute immunogenicity data about the study product and hence are excluded.

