## 5 Objectives and endpoints

### 5.1 Primary objectives and endpoints

*Primary objectives 1:*

- To evaluate the safety and tolerability of VRC07-523LS administered at 10 mg/kg IV infusion every 4 months
- To evaluate the safety and tolerability of VRC07-523LS administered at 30 mg/kg IV infusion every 4 months

*Primary endpoint 1:*

- Local and systemic Solicited AE signs and symptoms, laboratory measures of safety, Unsolicited AEs, SAEs, AEs of special interest (AESI) and rates of discontinuation

*Primary objectives 2:*

- To determine whether multiple infusions of VRC07-523LS reach and maintain detectable levels in the mucosa
- To correlate levels of VRC07-523LS in serum and the mucosa

*Primary endpoints 2:*

- Levels of VRC07-523LS in genital and rectal secretions, as well as cervical, vaginal, and rectal tissues at the collection timepoints
- Levels of VRC07-523LS in serum out to Week 48, 16 weeks after the last product administration

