## 6.3 Blinding

Participants and site staff will be unblinded as to participant treatment group assignments. VRC07-523LS concentration and ADA assessments will be performed in a blinded fashion.

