#### 6.4.3.4 Reasons for discontinuation of study product administration and early study termination

The number and percentage of participants who discontinue study product administration and who terminate the study early will be tabulated by reason and treatment arm.

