7 STATISTICAL ANALYSIS

This section describes the final study analyses, unblinded as to treatment arm assignment. All analyses pertaining to safety and drug levels objectives of the study will be conducted with an intent-to-treat analysis that includes all randomized individuals per their randomization allocation. Additional analyses will be performed that account for the actual infusions and dose levels that each participant received. Analyses for primary endpoints will be performed using SAS and R. Additional software may be used to perform non-compartmental PK and population PK analyses (eg, Monolix). All other descriptive and inferential statistical analyses will be performed using SAS, or R statistical software.

No formal multiple comparison adjustments will be employed for multiple primary or secondary endpoints. Unless otherwise noted, all statistical tests will be 2-sided and will be considered statistically significant if $p < 0.05$.

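### SAP 4 reduces the randomised cohort to infused participants, while SAP 7 and protocol 6.4 describe intent-to-treat of everyone randomised; those never infused should be reported by arm

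*SAP*

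**What the plan says.** **Cohort rule.** SAP 4 states: "Participants who are randomized but do not receive the study product are released from randomization", and draws the consequence itself: "so the randomized cohort will consist only of participants who received study product". It then calls the analysis modified intent-to-treat, on the ground that "individuals who are enrolled but not randomized do not contribute immunogenicity data about the study product and hence are excluded".

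**Analysis principle.** SAP 7 promises, for safety and drug-level objectives, "an intent-to-treat analysis that includes all randomized individuals per their randomization allocation". Protocol 6.4 uses the same words.

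**Conduct.** Under protocol 6.3, "Participants and site staff will be unblinded as to participant treatment group assignments". Protocol 9.3 places randomisation after the baseline mucosal collection and before the infusion, generally within 4 working days but possibly longer. Appendix F marks randomisation at the day -14 visit and the first infusion at day 0. Protocol 6.2 and SAP 5 keep recruitment open until 24 participants have been dosed.

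**Endpoint.** Primary endpoint 1 in protocol 5.1 ends with "AEs of special interest (AESI) and rates of discontinuation". Under protocol 6.4.3.4, counts and percentages for stopping product and for leaving the study early "will be tabulated by reason and treatment arm". No denominator is given.

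**The concern.** The two descriptions agree only if the word randomised is redefined by something that happens after randomisation, namely receipt of the first infusion. In a blinded trial with immediate dosing this would matter little. Here participant and site can know the assigned dose level before the infusion, so whether a person starts can depend on the arm. Anyone who does not start is released, and continued recruitment fills the place.

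Two things are at stake. The report could label as intent-to-treat a cohort selected after open assignment. And non-initiation, if it differed between 10 and 30 mg/kg, might not be visible by arm, although rates of discontinuation are listed in a primary endpoint. SAP 4's justification for the modification does not reach this case, because it concerns people who were never randomised.

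**Working it through.** **1. Who is in which set.** Take a participant who is enrolled, randomised, and never infused.

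| Place | Is this person included? |
|---|---|
| SAP 4, release rule | No |
| SAP 4, reason for the modification | Not addressed |
| SAP 7 and protocol 6.4, intent-to-treat statement | Yes, under the assigned arm |
| Protocol Table 3-1, meaning of N | No; N counts those with at least one infusion |
| Protocol 6.1.1, safety set | No; at least one administration is required |
| Protocol 6.4.3, who provides safety data | Names only those with a partial or complete administration |
| Protocol 6.4.3.4, discontinuation and early termination | Not stated |

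The protocol therefore carries both ideas: a treated-only safety set and an intent-to-treat statement covering all randomised. SAP 4 follows the first and SAP 7 repeats the second.

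**2. The plan's own precision figure.** Protocol 6.1.1 gives a 95% score upper bound of 24.2% for 0 events in 12. For zero events the bound is z²/(n + z²). With z = 1.96, z² = 3.8415, and 3.8415/15.8415 = 24.25%. The figure reproduces.

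**3. Effect of the rule on a by-arm rate.** The documents give no rate of non-initiation after randomisation, so the count k in one arm is an assumption. Suppose 12 are infused and nobody discontinues later. The exposed-only rate is 0/12. With all randomised as the denominator it is k/(12 + k):

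| k (assumed) | Infused only | All randomised | 95% score interval, all randomised |
|---|---|---|---|
| 0 | 0/12 = 0% | 0/12 = 0% | 0 to 24.25% |
| 1 | 0/12 = 0% | 1/13 = 7.7% | 1.37 to 33.31% |
| 2 | 0/12 = 0% | 2/14 = 14.3% | 4.01 to 39.94% |
| 3 | 0/12 = 0% | 3/15 = 20.0% | 7.05 to 45.19% |

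Each additional non-starter moves the arm's rate by about 6 to 8 percentage points. The intervals overlap widely, as they must with 12 per arm.

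**4. How likely is at least one case?** If each of 24 randomised people independently had probability r of not being infused, the chance of at least one is 1 − (1 − r)^24. For assumed r of 2%, 5% and 10% this gives 38%, 71% and 92%. These values show sensitivity and are not estimates for this trial.

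**The case against.** A fair defence runs as follows.

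- **Treated-only is the protocol's own safety set.** Table 3-1, 6.1.1 and 6.4.3 all use it, and a person never exposed says nothing about adverse events or drug levels. This stands. The AE and drug-level analyses should stay on infused participants.
- **SAP 7 can be read through SAP 4's definition.** On that reading both describe the same people and only the label is loose. This stands in part. But the label is then wrong, and the reason given for modifying it omits the people actually removed after randomisation.
- **This SAP version covers pharmacokinetics.** SAP 1 says it will be updated before the final safety analysis, and SAP 8 lists no discontinuation table. SAP 3.1 does not list discontinuation either, so that element rests on protocol 5.1. This stands as to timing. SAP 4 nonetheless already says how all safety data from randomised participants are to be analysed.
- **Discontinuation is descriptive.** It is one item in a list, the safety objectives treat each dose level separately, and no formal between-arm testing of unsolicited events is planned. This stands and limits the weight of the point.

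A reader might infer more: that people who decline after learning their assignment necessarily vanish from the primary discontinuation endpoint. The documents do not say so. Protocol 6.4.3.4 names no cohort. Refusing further participation counts as early termination under protocol 7.3.4. Enrolment precedes randomisation, and SAP 4 speaks of release from randomisation, not from the study. Omission from the by-arm table is a reasonable inference from SAP 4, but it remains an inference. Nor do the documents show that anyone would decline because of the arm. Protocol 9.3 also keeps those unwilling to continue after the baseline biopsies from being randomised at all.

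**Conclusion.** The inconsistency is real and should be corrected. SAP 4 defines an exposed-only cohort by a post-randomisation event in an open trial, while SAP 7 and protocol 6.4 call the analyses intent-to-treat with everyone randomised. Followed as written, the rule would put the wrong name on the cohort and could leave arm-related non-initiation unreported by arm.

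The consequence is limited. Adverse-event and drug-level results do not change. The effect falls on disposition and on how the discontinuation rate is read. Its size is unknown and may be zero; one assumed case changes an arm from 0% to 7.7%. The conclusion rests on the plain wording of the sections compared, and on the inference that SAP 4's cohort would supply the denominator that protocol 6.4.3.4 leaves open.

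**What to change.** At the SAP update planned before the final safety analysis:

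1. Remove the release rule from the analysis-set definition in SAP 4, and keep every randomised participant in the dataset with the assigned arm.
2. In the disposition table, report participants randomised but never infused by arm and reason, with all randomised as the denominator. Show this next to the discontinuation rate among those infused, and state both denominators.
3. Keep adverse-event and drug-level analyses on participants with at least one partial or complete infusion. Name that set *modified ITT (exposed)* in SAP 4, SAP 7 and protocol 6.4, in place of the present intent-to-treat wording, and give as its reason the absence of exposure. Protocol 6.4.4.1, which applies the MITT label to data from enrolled participants, should be aligned.

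The cost is wording in two documents and one extra table row. The discontinuation figure may look slightly less favourable. Recruitment, sample size and the adverse-event and drug-level results are unaffected.

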5 RANDOMIZATION

Participants will enroll in the study at the first biopsy collection. Only participants who remain in the trial after the completion of the first biopsy visit will be randomized.

Accrual will continue until 24 participants have received first product administration.

The randomization sequence will be obtained by computer-generated random numbers and provided to each HVTN CRS through the SDMC via a Web-based randomization system.

Groups 1 and 2 will be randomized simultaneously.

The randomization will be stratified by assigned sex at birth and done in blocks to ensure balance across both groups.

6 BLINDING

Participants and site staff will be unblinded as to participant treatment group assignments. VRC07-523LS concentration and ADA assessments will be performed in a blinded fashion.

7 STATISTICAL ANALYSIS

This section describes the final study analyses, unblinded as to treatment arm assignment. All analyses pertaining to safety and drug levels objectives of the study will be conducted with an intent-to-treat analysis that includes all randomized individuals per their randomization allocation. Additional analyses will be performed that account for the actual infusions and dose levels that each participant received. Analyses for primary endpoints will be performed using SAS and R. Additional software may be used to perform non-compartmental PK and population PK analyses (eg, Monolix). All other descriptive and inferential statistical analyses will be performed using SAS, or R statistical software.

No formal multiple comparison adjustments will be employed for multiple primary or secondary endpoints. Unless otherwise noted, all statistical tests will be 2-sided and will be considered statistically significant if $p < 0.05$.

8 PHARMACOKINETICS TABLES AND FIGURES, BY ASSAY

8.1 Serum Concentration and Pharmacokinetics Analysis

VRC07-523LS levels will be measured in serum collected at the designated timepoints and in female and/or male assigned sex at birth.

The method for detection of VRC07-523LS utilizes Carboxylated magnetic beads (Magplex, Luminex) are covalently coupled to NeutrAvidin and are then subsequently bound to a biotinylated goat anti-mouse IgG Fc antibody. This is then followed by the binding of the 5C9 anti-idiotype monoclonal. Through this process, 5C9 is oriented to freely bind to the paratope of the VRC07- 523LS. The sample is then added to the coated beads and incubated for 120-125 minutes in a plate shaker. At the end of the incubation, plates are washed using BAMA wash buffer. Bound VRC07-523LS is detected using a goat anti-human IgG Fc, multi-species serum protein (SP), conjugated to phycoerythrin (PE). Microspheres are read on a Bioplex 200

instrument to measure Fluorescence Intensity (FI). Mean Fluorescence Intensity (MFI) values are used to quantify VRC07-523LS that has been bound to 5C9 anti-idiotype antibody in solution. VRC07-523LS IgG standard curves are run on each plate to quantify VRC07-523LS IgG in human serum and mucosal test samples. Standard curves are fit to a 5-PL logistic regression to convert MFI of samples to VRC07-523LS IgG mAb concentration. Duplicate wells containing HIV-1 seronegative normal human reference serum and negative control beads are also run in each assay to ensure specificity of binding.

All samples will be shown in the plot, including concentrations below the lower limit of quantification (LLOQ). Samples with concentrations above the LLOQ at a 1:100 dilution will be further tested at various dilution factors to obtain MFI's in the linear range of the standard curve, and the in-well concentration closest to the EC50 of the 5PL standard curve will be reported.

Several criteria will be used to determine if data from an assay are acceptable and can be statistically analyzed. The standard curve EC50 values and MFI values will be tracked against historical data using Levey-Jennings charts and points with an MFI > 100 must have a %CV <20% between replicates. Any sample without at least 2 observed concentrations in agreement with each other, or with baseline MFI > 1000 will be repeated to obtain an accurate measurement.

8.1.1 List of Tables

- Table 1, Counts of concentrations > LLOQ

- Table2, Descriptive statistics (i.e., sample size (N), geometric mean, median, min, max and IQR) of participant-level mAbs concentrations by treatment groups, visits, among the per protocol cohort, including values below the LLoQ.
- Comparison of dose-normalized concentrations between groups within time points

8.1.2 List of Graphs

- Figure 1: Boxplots of the VRC07-523LS concentrations by visit day and treatment groups. Within each treatment group panel, boxplots of VRC07-523LS concentrations will be displayed side by side against the visit day.
- Figure 2: Spaghetti plots of VRC07-523LS concentrations by treatment group over visit day at the individual- and at group-level (median and geometric mean). VRC07-523LS concentrations from each treatment group will be overlaid in the same panel with different colors. Individual-level concentrations will be displayed in grey lines and group-level in solid colored lines.
- Figure 3: Spaghetti plots and boxplots of does-normalized VRC07-523LS concentrations by treatment group over visit day.

8.2 Anti-Drug Antibodies (ADA)

To address Secondary Objective 2 of the study, anti-drug antibody (ADA) detection and characterization assays will be run to evaluate whether infusion of VRC07-523LS may induce an antibody response that target the study product and/or whether some subjects exhibit anti-drug reactivity prior to infusion, for each desired participant specimen of the study protocol.

Antidrug antibodies (ADA) are most typically detected and characterized using a tiered testing strategy. In Tier I, a sensitive binding assay is used to determine if samples may have ADA present. In Tier II, the response is confirmed, typically by establishing the specificity of the response by competition with free drug. In Tier III, the response is characterized, typically with a neutralization reduction assay and/or a titering assay. For Tiers I and II as well as the titering assay, “bridging” assay formats are amongst the most common.

A bridging assay to detect ADA against a biologic drug product begins with covalently conjugating drug product with either biotin or the Sulfo-Tag label. Biotinylated and Sulfo-Tagged mAb are then combined and mixed with serum that may contain ADA. When an ADA response is present, complexes comprised of the ADA and one or both types of labeled mAb species can form. In some cases, because antibodies are multivalent, the ADA will act as a bridge between the biotinylated and Sulfo-Tagged drug in a ternary complex. Following an incubation to allow complex formation, this mixture is added to a proprietary streptavidin-functionalized plate, washed, and the presence of ADA responses, as indicated by the presence of ternary or “bridged” complexes, is detected. The Meso Scale Diagnostics (MSD™) instrument passes an electrical current through the plate, exciting any Sulfo-Tag within proximity of the plate surface, and resulting in electrochemiluminescence, which is expressed in relative light units (RLU). During assay qualification, a positivity cut point is established and utilized to determine whether a sample is ADA Screening Assay positive based on its RLU signal intensity. While only complexes containing both biotinylated and Sulfo-Tagged drug will result in signal, additional complexes are likely to form that are nonconductive to signal measurement (e.g. biotin:biotin or Sulfo-Tag: Sulfo-Tag bridged products). Formation of these nonproductive complexes has been taken into consideration during the development phase, and efforts have been made to maximize sensitivity by reducing the likelihood of formation of these nonproductive complexes. The criteria for establishing positivity cut points in the Tier I assay are designed to minimize the risk of false negatives. As such, a certain proportion of ADA-negative subjects will be classified as positive in

this screening assay but can later be investigated with Tier II confirmatory and, in some cases, Tier III characterization assays. The assays are all performed in 96well plates for high throughput capacity. The screening assay has been qualified, and the specificity and titering assays have been deemed fit for purpose.

All designated serum samples will be assayed at a 1:12 dilution of serum for Tiers I and II. In Tier III, titers will be defined as lowest fold dilution from a starting dilution of 1:12 at which the test sample remains above the assay cut point.

Screening assay

- i. If the average value of a test sample exceeds the assay cut point, that sample is classified as Tier I positive.
- ii. %CVs are calculated by the Discovery Workbench Software. If any control exceeds an average CV of 20%, an investigation of the run will be required. If any sample exceeds a CV of 20%, that sample will need to be rerun.

Confirmation assay

- i. Tier 1 positive samples are retested in the presence of free drug. If free drug reduces signal by more than the specificity threshold, these samples are considered Tier II confirmed.

Titering assay

- i. Test samples that are Tier II confirmed will be titrated using the screening assay across a dilution series. The lowest fold dilution at which the test sample remains above the assay cut point is considered its titer.

The following evaluation criteria will be employed for screening, confirmatory and tittering assays:

- i. %CVs must be below 20% for sample replicates
- ii. Positive controls must exceed values established during qualification

ADAs will be categorized as treatment induced, boosted, or independent based on the longitudinal profile observed, with boosted responses defined by a 3-fold increase in titer from baseline. Any sample that was either Tier I or Tier II negative at baseline, then Tier II positive at a later timepoint is considered as induced ADA. Only samples that were ADA positive at baseline have their titers compared to follow up timepoints to determine if a response is boosted or independent.

The statistical analysis tabulates frequencies of serum samples in which ADA were detected, along with their 95% confidence intervals, by treatment group, timepoint, and ADA assay tier. The analysis will also report summary statistics (e.g., mean, median, range, as appropriate) of ADA levels among samples with detectable ADA levels.

If ADA is detected in more than one sample, the percentages of participants with detectable ADA levels, along with their 95% confidence intervals, will also be plotted as a function of time by treatment group.

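### SAP 8.2 defines the ADA titer as the lowest dilution above the cut point, probably a slip for highest; as written, no baseline-positive participant can be classed as boosted

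*SAP*

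**What the plan says.** SAP section 8.2 sets out three ADA tiers.

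- **Dilution in Tiers I and II:** "All designated serum samples will be assayed at a 1:12 dilution of serum for Tiers I and II".
- **Tier I (screening):** "If the average value of a test sample exceeds the assay cut point, that sample is classified as Tier I positive".
- **Tier II (confirmation):** "Tier 1 positive samples are retested in the presence of free drug"; a large enough drop in signal confirms the sample.
- **Tier III (titering):** "Test samples that are Tier II confirmed will be titrated using the screening assay across a dilution series".

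The titer is defined twice. The general description says that "titers will be defined as lowest fold dilution from a starting dilution of 1:12 at which the test sample remains above" the cut point. The titering paragraph says: "The lowest fold dilution at which the test sample remains above the assay cut point is considered its titer".

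The titer then feeds a classification, with "boosted responses defined by a 3-fold increase in titer from baseline". The comparison is restricted: "Only samples that were ADA positive at baseline have their titers compared to follow up timepoints to determine if a response is boosted or independent".

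Protocol section 10.4 mentions titration but does not define a titer. Section 10.5 covers only the functional assay.

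**The concern.** An end-point titer measures how far a sample can be diluted before its signal falls to the cut point, so it is the *highest* dilution still above it. The SAP takes the other end of the series. The lowest dilution is the starting one, and a sample reaches titration only if it has already read positive there. The definition therefore returns a constant.

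SAP 8.2 names anti-drug reactivity before infusion as one of the questions the assays should answer. Titer is the only criterion it gives for deciding whether such reactivity was boosted by treatment or was independent of it. With a constant titer, every comparable baseline-positive participant falls into the independent class. The Tier III line plot in 8.2.2 would carry no information, nor would any summary of ADA levels based on titer.

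Secondary endpoint 2 is worded as a serum ADA concentration. Apart from raw signal in relative light units, titer is the only graded measure of ADA amount that 8.2 defines. The SAP does not say which of the two its summary of ADA levels will use, so this last consequence is conditional.

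**Working it through.** The documents give no figure to reproduce here. The check applies the rule to the samples the SAP sends to titration.

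**Inputs, all from SAP 8.2:** Tiers I and II run at 1:12; Tier I positive means above the cut point; only Tier I positives go to Tier II; only Tier II confirmed samples are titrated, with the screening assay, from 1:12; boosted means a 3-fold titer rise, assessed only in baseline positives.

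**Step 1: the rule as written.** Titer = min{d in the series, d ≥ 12 : signal(d) > cut point}. For a sample above the cut point at d = 12, the minimum is 12. This holds for any dilution step and any shape of dilution curve.

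**Step 2: the ratio.** Follow-up titer / baseline titer = 12/12 = 1, which is below 3. From a baseline titer of 12, a boosted call needs a follow-up titer of at least 3 × 12 = 36. The rule cannot return that value for a sample positive at 1:12.

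**Step 3: the rule as presumably meant.** Titer = max{d in the series : signal(d) > cut point}. The SAP does not state the dilution step, so 2-, 3- and 4-fold steps are assumed for illustration. Take a signal inversely proportional to dilution, a baseline sample at 2 times the cut point at 1:12, and a 10-fold rise (20 times the cut point). The baseline sample stays above for d < 2 × 12 = 24 and the follow-up sample for d < 20 × 12 = 240.

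| Assumed step | Series | Lowest: baseline, follow-up, ratio | Highest: baseline, follow-up, ratio |
|---|---|---|---|
| 2-fold | 12, 24, 48, 96, 192, … | 12, 12, 1 | 12, 192, 16 |
| 3-fold | 12, 36, 108, 324, … | 12, 12, 1 | 12, 108, 9 |
| 4-fold | 12, 48, 192, 768, … | 12, 12, 1 | 12, 192, 16 |

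As a more extreme case, end points of 12 and then 12,288 (ten doublings) give an end-point ratio of 12,288/12 = 1,024, yet the written rule still gives 1.

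**Step 4: exceptions.** A confirmed sample near the cut point may read below it at 1:12 on titration. If signal falls with dilution, no dilution is then positive and the titer is undefined, not 3-fold higher. A hook effect does not rescue the rule: a sample positive at 1:12 in spite of the hook still gets 12, and one negative at 1:12 is Tier I negative and is never titrated. A titer above 12 would need a result in the titration run that disagrees with the screening run, which is an assay artefact.

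**Step 5: reach.** Protocol Appendix E appears to schedule ADA testing at visits 2, 5, 7 and 9. The ceiling is therefore 24 × 4 = 96 samples and 24 × 3 = 72 baseline-to-follow-up ratios. The real number of ratios is smaller, since only baseline positives are compared. SAP 8.2.1 and 8.2.2 list 2 tables + 2 graphs = 4 ADA outputs, of which 1 uses titer. The boosted/independent label appears only in the text of 8.2.

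**The case against.** The strongest reply is that this is a wording slip that would not change any result. The reference to the sample remaining above the cut point, the dilution series and the 3-fold rule make sense only for an end-point titer, and a laboratory would probably run one. Protocol section 14 also lists a laboratory assay algorithm, available on request, that may govern how titers are read. Few participants may be concerned: prior recipients of anti-HIV antibodies are excluded (Protocol 7.2), and Protocol 4.8 lists ADA among the reactions not observed to date with VRC01-class antibodies. The 96 and 72 are ceilings, not expected counts.

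Most of this stands and limits the weight of the point. Protocol 4.8 concerns responses to product rather than pre-existing reactivity, so it does not show that there will be no baseline positives, and the documents give no rate. What does not stand is the idea that the text needs no correction. The SAP is the prespecified rule from which programmers and outside readers work, it states the wrong end of the series twice, and the algorithm is only listed, not reproduced. *Lowest* could be read as lowest serum concentration, which would be the highest fold dilution, but the text says fold dilution.

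**Conclusion.** The concern holds. Followed as written, the definition gives a titer of 12 for every sample that reads above the cut point at 1:12 on titration. Every ratio is then 1 against a threshold of 3, and the boosted class is empty whatever the rise. This follows from the SAP's own tier rules and needs no assumption about dilution step or baseline-positive rate. It does assume that the titration run agrees with the screening run at 1:12; where it does not, the ordinary outcome is no titer rather than a boosted one.

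The damage is confined to the boosted/independent split, the Tier III line plot and any titer-based summary of ADA levels. Secondary objective 2 (whether ADA is detectable), the Tier I and II response rates, the list of Tier II confirmed participants and treatment-induced ADA are unaffected. The point is minor, with high confidence about the wording and its literal consequence. Whether anyone would have applied it literally cannot be judged from the documents.

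**What to change.** In both sentences of SAP 8.2 replace *lowest* with *highest*, so that the titer is the highest fold dilution, in the series starting at 1:12, at which the sample is still above the assay cut point. Leave the 3-fold rule as it is.

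Two clarifications would help but are not part of the error and may already be in the laboratory's algorithm: state the dilution step, and say how a Tier II confirmed sample that reads below the cut point at 1:12 on titration is handled.

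The cost is one word in each of two sentences, with no new samples, assays or analyses. SAP section 1 already plans a review and update before additional immunogenicity analyses, which is a natural time to make the change.
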